6.0 Study Population, Selection, Withdrawal/early exit

6.1 Study Population: This is a community based trial. The study population will be drawn from patients who are seeking or have previously sought treatment of primary or secondary lower extremity lymphoedema. Only patients who meet the inclusion criteria listed below will be considered for participation.

6.1.1 Inclusion Criteria: Subjects may participate in this study if they meet **all** of the criteria described below:

- Subjects must be \geq 18 years old
- Subjects must have a diagnosis of primary or secondary Stage 2 unilateral or bilateral lower extremity lymphoedema.
- Must currently be using adequate compression garment(s) as determined by the clinician:
 - Garments must be at least 20mmHg and no more than 3 months old and must be worn upon rising and removed at bedtime.
- Subjects must have clinically relevant excess limb swelling as determined by clinician “pitting test”.
- Must be able to attend all required in-clinic treatment visits

6.1.2 Exclusion Criteria: Subjects will be ineligible for this study if they meet any of the criteria described below:

- Diagnosis of active or recurrent cancer, or less than 3 months at the time of initial evaluation from the completion of chemotherapy, radiation therapy or primary surgery for the treatment of cancer.
- Active infection or inflammation
- Active thrombophlebitis (within the last 2 months)
- History of pulmonary embolism (within the last 2 months)
- Documented history of deep chronic venous insufficiency or deep venous obstruction with a reflux duration of > 2 second in the deep system, and any history of deep vein thrombosis (DVT)
- History of pulmonary edema
- History of congestive heart failure
- History of chronic kidney disease with a glomerular filtration rate (GFR) of less than 30 mls per minute.
- Patients with poorly controlled asthma (i.e. those with severe persistent symptoms throughout the day, night time awakenings

several times per week, use of a beta2 agonist inhaler several times per day and those whose normal activity is extremely limited).

- Symptomatic or severe peripheral artery disease, defined by current lifestyle-limiting claudication or critical limb ischemia
- Presence of an open wound or ulcer of any etiology
- Diagnosis of lipoedema and lipolymphoedema*
- Currently using an in home pneumatic compression device
- Metal implants that would interfere with bio impedance equipment
- Individual with pacemaker or other implanted electronic devices
- Inability or unwillingness to remove bandaging from treatment regimen while participating in the study.
- Pregnancy
- Any condition where increased venous and lymphatic return is undesirable
- Inability or unwillingness to participate in all aspects of study protocol and/or inability to provide informed consent
- Currently participating in another clinical trial
- Currently using diuretics
- BMI > 40

6.1.3 Exit/Discontinuation Criteria: Subjects may exit the study prior to completion of all study visits if they meet any of the following criteria. The data collected as part of the study will be included in the intent to treat analysis.

- Subject death
- Subject voluntarily withdraws
- Subject experiences a serious adverse event that in the investigator's clinical judgment necessitates study discontinuation
- Subject acquires any of the exclusion criteria during treatment phase of the study

** Clinical assessment of lipoedema and lipolymphoedema will be completed to assure that the subject meets enrollment criteria. Lipoedema is a type of lipodystrophy, which can cause enlargement of the legs and be confused with lymphoedema. It is a clinical diagnosis with no specific diagnostic tests available. The typical pattern of lipoedema is excess fat deposition in the lower part of the body from the hips to the ankles, commonly with a history of bruising and tenderness. Patients also exhibit asymmetrical weight loss on dieting with weight being lost in the upper part of the body rather than the legs. Pure lipoedema is non pitting.*

Lipolymphoedema is the term used when patients with lipoedema develop superadded oedema. This typically forms around the ankles and feet and is pitting in nature. The diagnosis of lipolymphoedema is made by applying the

diagnostic criteria for lipoedema but with the presence of pitting oedema in the ankles and feet.

6.2 Recruitment and Randomisation

6.2.1 Recruitment Plan: Subjects will be recruited from patients either seeking or who have previously sought treatment at a clinic for lymphoedema. Desired enrollment/follow-up time (first subject in to last subject out) is 20 weeks. If additional recruitment is required to meet enrollment, referring general practitioners and potential reference clinics may be solicited for subjects. Patient advocacy/support groups may also be notified of the study opportunity. Subject recruitment materials may be provided for referring physicians' waiting rooms including posters, flyers, brochures, etc. If additional recruitment is required, direct to public advertisements in local newspapers may be utilized.

6.2.2 Randomisation Scheme: After completing the informed consent, subjects will be randomly assigned equally to one of three groups. Randomisation will follow the computer generated scheme. A master copy of the scheme will be kept at TSTI.

The site(s) will be provided with sealed envelopes containing the device assignment for each potential subject. Each envelope will be numbered sequentially from 01 to 030. Randomisation envelopes and/or subject IDs cannot be used more than once. After the subject signs the informed consent agreeing to participate in the study, the appropriate study staff will obtain the next sequential sealed randomisation envelope and open it while the subject is present.

The randomisation assignment cannot be changed or chosen by the subject or the investigator. The randomisation envelope should be placed in the subject binder.

6.3 Study Timetable:

Task	25 Weeks				
	1-5	6-10	10-15	15-20	21-25
EC/Regulatory	X	X			
Enrollment		X	X	X	
Treatment		X	X	X	X
Data Entry		X	X	X	X
Data Analysis				X	X

7.0 Treatment Plan and Study Procedures:

7.1 Dosage and Rationale: All subjects enrolled will receive treatment to the study leg using the FT study device. The treatment will be received in clinic and the garments applied by a trained clinician with the exception of Group A's weekend treatment which will be done by the patient in their home.

Subjects will be randomised into one of three groups. Following randomisation and study arm assignment the subjects will receive treatment according to study arm assignment:

Group A: subjects will receive 12 consecutive days of treatment utilizing the following treatment regimen. The first 5 days will be in clinic (Monday through Friday) followed by self administered at home treatment for 2 days (Saturday and Sunday). The last 5 days of treatment will be in clinic ending the treatment phase on day 12 (Monday through Friday).

- One lower extremity treatment per day using program L1 with the pressure set to "normal" applying the full garment set.

Groups B & C subjects will receive 5 consecutive days of treatment in clinic (Monday through Friday) utilizing the following treatment regimens.

- Group B: Two lower extremity treatments per day (am and pm) using program L1 with pressure set to "normal" applying the full garment set.
- Group C: Two consecutive treatments 2 times a day (am and pm) using program L1 with pressure set to "normal" applying the full garment set.

In the case of bilateral lymphoedema, the leg with the largest volume will be considered the study leg. The contralateral (non study) leg will be treated in the same manner that it was being treated prior to entering the study. Limb volume measures for both legs will be collected.

At the screening visit, each subject's compression garment(s) will be assessed for clinical adequacy (Class: $\geq 20\text{mmHg}$; Age: 3 months or less) by the Principal Investigator. Subjects will be instructed to wear the compression garment(s) every day during wakeful time. Garments may be removed while bathing and overnight. The clinician will remove the subject's compression garment during device treatment. This treatment regimen is consistent with standard home care compression garment(s) treatment.

7.2 Subject Data Requirements: The following data will be collected from all subjects:

Key: B = Before Treatment A = After Treatment D = During Visit	Screening	Baseline/ Initial Treatment (D1)	Treatment (≠ D1, 5 & 12)	Day 5(All Groups) and Day 12 (Group A)
Medical History	D			
Bio Impedance		B A	B A	B A
Perometer		B A	B A	B A
Duplex U/S	B			
Interface Pressure		B	B	B
Ultrasound		B		A
Tonometry		BA	BA	BA
Moisture Meter D		B A*	B A*	B A*
Subject Interview				D
MyMOP		D		D
Activity Level		D	D	D
BMI		D	D	D
Adverse effects		A	A	A
Compliance		D	D	D

*Group C: Will have moisture meter done before the first treatment session, after the first treatment session, and then after the final treatment session of the day = 3 times total during treatment visits.

7.3 Laboratory Testing Procedures: After provision of informed consent, women of child bearing potential will be tested for pregnancy at the site specific clinical laboratory according to site standard procedures. If the pregnancy test is positive, subjects will be excluded from the study.

Potential subjects suspected to have renal dysfunction will undergo a blood test to determine the glomerular filtration rate (GFR). Those subjects with a GFR of less than 30mls per minute would be excluded from the study.

7.4 Clinical Study Procedures: Pre-screening of subjects will be conducted by study staff either by phone or in person. Potential subjects will meet with study staff in-person for the consent process.

7.4.1 Informed Consent: Informed consent must be obtained from all subjects prior to randomisation and participation in clinical studies as mandated by Federal Regulations and/or the qualifying Ethics Committee (EC). A blank copy of the EC-approved informed consent form must be kept on-site and by the sponsor. The signed original for each subject must be kept in the subject's medical

records and copy of the signed informed consent will be provided to the subject.

A copy of the consent will be given to the subject to read and take home to consider if they prefer. All the subject's questions will be answered, prior to signing the informed consent. No research procedures will be performed until subject signs the consent. A signed copy of the consent will be provided to the subject. After completing the informed consent, subjects will be randomly assigned equally to one of 3 groups.

7.4.2 Duplex Ultrasound: This test will be done at the time of the screening visit to rule out a significant deep vascular obstruction or venous insufficiency as determined by a reflux of > 2 second. If the subject had a duplex U/S done within the last two months the results may be reviewed and utilized for inclusion or exclusion into the study. The test has no associated risks. A water soluble gel is placed in a handheld transducer, which directs high-frequency sound waves to the arteries or vein being tested. Subject should experience no pain or discomfort.

7.4.3 Bioelectrical Impedance: A Bioimpedance Spectroscopy (BIS) device will also be used to quantify changes in intra- and extra-cellular fluid at each visit. BIS utilizes the characteristics of frequency dependent current flow to detect fluid changes. Measurements are generated by a low frequency electrical signal transmitted to the patient from the device through skin surface electrodes. The measurement is imperceptible to the subject and is not confounded by weight or muscle changes that may occur in the limbs. Appendix B contains the study procedure for bioimpedance.

7.4.4 Limb Volume Measurement: Limb volume measures will be taken at each visit for both legs of the subject. The site will conduct limb volume measurements using an optoelectronic system (Pero-System, Perometer, Appendix C). The perometer utilizes infra red light beams to measure limb volume more rapidly than the circumferential tape measure method. These systems have been validated against circumferential measures to a correlation coefficient of .977 in leg subjects.¹⁷ The perometer can be used for whole leg or segmental (upper/lower) measurements. Perometer measurement will be taken twice on each leg and the average used.

7.4.5 Tonometry: Tissue assessment/fibrosis will be evaluated with use of a tonometer at anatomically defined locations on the affected leg and on the trunk. The Tonometer is a mechanical device that gives

an indication of the resistance of tissue to compression. It is used in lymphoedema to give an estimate of the extent of pitting and fibrotic induration. Tonometry readings of the affected areas will be compared to readings taken pre-treatment intervention. Appendix D contains the Tonometer operating instructions and the body points for this trial.

7.4.6 Tissue Ultrasound (U/S): Tissue ultrasound will be used to measure skin thickness and oedema in fixed areas of the limb and trunk at Day 1 (pre-treatment) and at the day 5 (All Groups) and day 12 (Group A) post FT treatment. Measurements will be obtained at defined anatomic locations. The aim of this is to measure and assess for changes in the tissue in the treated limb and trunk. A positive correlation has been observed between skin thickness and oedema in the affected lymphoedema arm. In addition, increases in skin thickness may also be related to development of fibrosis or other skin changes. The use of ultrasound has been suggested in the literature as another simple, reliable means to evaluate therapeutic outcomes.¹⁸

7.4.7 Other Measures:

Local tissue water (LTW) measures will be obtained with a Moisture Meter D™ (Delfin Technologies, Finland). This device and technology has been demonstrated to provide a measure of LTW and its change based on measurements of the skin's tissue dielectric constant at a frequency of 300 MHz. The method has been widely used in clinical studies to evaluate LTW and its change under a variety of conditions.¹⁹⁻²² (Appendix E)

Interface pressure will be obtained with the PicoPress®. This technology was designed to be used to determine the pressure exerted under both static and dynamic compression. The PicoPress® transducer allows for dynamic pressures readings.²³ Appendix F

Symptom assessment will be obtained by using the Measure Yourself Medical Outcome Profile (MyMOP). This questionnaire was created to be a patient-generated or individualized outcomes questionnaire. It was designed to be problem specific but also include general wellbeing questions. Patient symptoms can be emotional, social or physical (Appendix G). At the conclusion of study treatment visits the subject-reported treatment comfort and effectiveness will be assessed by asking the subject targeted questions. (Appendix H)

Activity level will be monitored through the use of a pedometer and a subject diary. The subject wear a pedometer during the treatment phase of the study to record the number of steps accumulated throughout the day. The diary is intended to capture additional information regarding the subject's activity level such as type of activity.

7.4.8 Screening Visit: At this visit, the patient will be asked to provide written informed consent and inclusion and exclusion criteria will be evaluated to ensure that the patient meets all entrance criteria. See section 7.2 for a schedule of events.

After the informed consent process is complete, the subject will be randomised into one of 3 study groups. The baseline visit must occur on a Monday. Study staff and the subject will make every attempt to schedule all study visits at the same time of day.

At this visit, the subject will withdraw all at home lymphoedema treatments with the exceptions of wearing appropriate compression garments and maintaining proper skincare. Subjects cannot use limb bandaging at any time during the study.

The subject will leave the screening visit with:

- Schedule for all study visits with the first treatment visit starting on a Monday.
- Pedometer and instruction to start wearing the morning of the first treatment visit
- Diary to record daily activity and instructions to start documenting the morning of the first treatment visit
- Contact information and instructions to call if any problems arise

7.4.9 Baseline Visit/Initial Treatment: At the time of the baseline/initial treatment visit the subject will undergo the study procedures according to the table in section 7.2.

During the visit the subject will undergo treatment according to which group they were randomised. For Groups B and C which receive FT treatment twice a day the subject must have at least 2 hours and no more than 6 hours between the am and pm treatment sessions. The compression garment must be worn between the am and pm treatment sessions.

7.4.10 Treatment Visits (Group A: Day 2 to 5; 8 to 12; Group B & C: Day 2 to 5): The subject will be examined, receive FT

treatment according the treatment group assigned and the study parameters according to the table in section 7.2 will be completed and recorded by appropriately trained study staff.

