5.0 Study Design

5.1 Overview of Study Design: This study is a 3 arm, prospective, randomised, proof of principle clinical trial to determine the optimal treatment duration for achieving a measurable physiologic effect on lower extremity lymphoedema with the Flexitouch® system (FT) as determined by bioimpedance, perometry, tonometry, ultrasound, local tissue water assessment, symptom burden and subject interview.. Each intervention arm will include 10 completed subjects for a total of 30 completed subjects.

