12.0 General Study Information

12.1 Technical Support: Training and support for study procedures will be provided by the Sponsor contact listed in Section 1.1 or designee.

12.2 Discontinuation of the Study: The study may be terminated if:

- That the rate of severe adverse events in any arm of the study is such that the Ethics Committee decides continued participation would compromise subject safety. If deemed necessary by the Ethics Committee, a follow-up safety analysis will be performed for all subjects.
- Target subject accrual has not met, and cannot meet subsequent trial objectives.

Upon study termination by Sponsor, Sponsor will compensate Institutions for actual Study costs incurred through the close out of the Study, in accordance with the terms of the study contract.

12.3 Record Retention: Records must be maintained for a period of at least ten years after the date on which the study is completed or terminated. Investigator or Institution shall notify Sponsor at least thirty (30) days prior to any planned archiving or destruction of records related to this study. The recordings from the patient interviews will be transcribed and the recording then deleted. The transcription will be maintained with the study records.

12.4 Quality Assurance Procedures: This study will be conducted in accordance with Good Clinical Practice and International Conference on Harmonization Guidelines, NHS Trusts, institutional research policies and procedures and other appropriate regulatory requirements to ensure subject safety and quality of clinical procedures related to the conduct of the clinical trial. The investigators will permit regular monitoring, audits and site inspections by the EC, the sponsor, government regulatory bodies and any institution compliance and quality assurance groups of all study related documents (e.g. source documents, regulatory documents, data collection instruments, study data, etc.). The investigator will ensure the capability for inspection of applicable study related facilities. Regular trial monitoring will be conducted to ensure compliance to this protocol.

12.5 Materials Provided by the Sponsor: Sponsor will provide administrative study materials along with the FT controllers and garments, PicoPress® and pedometers.

12.6 Materials Provided by the Site: Institution will provide assessment equipment (scales, lab tests, perometer, bio impedance equipment, tonometer, clinical and support staff) needed to complete the trial.

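### The plan neither separates measuring from treating staff nor describes any masking for tonometry, tissue ultrasound, moisture-meter readings or covariate selection, although cheap partial masking is available

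*Combined protocol and SAP*

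**What the plan says.** Section 5.1 gives the design as follows: "This study is a 3 arm, prospective, randomised, proof of principle clinical trial". It says nothing about blinding.

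On allocation, section 7.4.8 states for the screening visit: "After the informed consent process is complete, the subject will be randomised into one of 3 study groups". Under section 6.2.2, staff "obtain the next sequential sealed randomisation envelope and open it while the subject is present". Baseline measurements come later, at the Day 1 visit (7.4.9).

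On roles, section 7.1 says: "The treatment will be received in clinic and the garments applied by a trained clinician", apart from Group A's weekend sessions at home. Section 7.4.10 covers examination, treatment and measurement in one sentence, with the parameters "completed and recorded by appropriately trained study staff".

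On the measures:
- **Tonometry (7.4.5):** a mechanical device applied at defined points on leg and trunk, compared with pre-treatment readings.
- **Tissue ultrasound (7.4.6):** "Tissue ultrasound will be used to measure skin thickness and oedema in fixed areas of the limb and trunk at Day 1", then after treatment on Day 5 in all groups and on Day 12 in Group A. The section does not say whether images are stored or who measures them.
- **Moisture meter (7.4.7 and the 7.2 table):** before and after treatment. A footnote gives Group C an additional reading: "Will have moisture meter done before the first treatment session, after the first treatment session", and again at the end of the day.

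On analysis, section 8.2.1 forces group and day into the model and lists six further covariates to be tried for entry. It gives no entry rule and does not say whether the analyst knows the arms. Section 8.2 says the trial is to show which endpoints respond most to dose, guide the next primary endpoint and supply an effect size for the next sample size.

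**The concern.** Anyone who takes or reads a measurement may know the subject's arm from screening onward, including at the Day 1 pre-treatment reading. Nothing stops them seeing the earlier value. The within-day outcome is a post-minus-pre difference on the same day, so sight of the first reading bears directly on the outcome.

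Such influence would not be equal across endpoints. A hand-placed tonometer or an ultrasound thickness measurement leaves more to the operator than a bioimpedance readout. A pilot that ranks endpoints by their response to dose could then credit an endpoint with sensitivity that partly reflects how it was read. The inflated effect would carry into the next trial's sample size.

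Covariate choice has a similar weakness. Six optional covariates, each in or out, allow 2^6 = 64 models per endpoint. An analyst who sees arm labels while choosing can be led, without intending it, towards the clearest contrast.

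**Working it through.** There is no planned figure to reproduce: the plan states no alpha, power, SD or expected effect, and section 8.2 says the study is unpowered for any single outcome. The check therefore has a reading part and an illustrative part.

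**Which outcomes are exposed**

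| Measure | Place in section 8.2 | Exposure to the operator |
|---|---|---|
| Bioimpedance | Fluid dynamics; expected to be most informative | Instrument readout; lower |
| Perometry | Fluid dynamics | Optoelectronic, taken twice and averaged; lower |
| Moisture meter | Fluid dynamics | Local reading at a site; higher |
| Tonometry | The only measure analysed for tissue density (8.2.2) | Hand-applied; higher |
| Tissue ultrasound | Listed in 5.2 and 8.1; no analysis in 8.2 | Hand-acquired, thickness measured; higher |

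The exposed measures thus include one in the top-ranked category and the only one modelled in the second.

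**Illustration of size**

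Input from the documents: 10 completed subjects per arm (5.1, 8.2). Assumptions, not in the documents: a reading shift of 0.2 to 0.3 SD in favour of one arm; a true difference of 0.5 SD, with 0.8 SD as a second case; two-sided 5% test; 80% power.

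1. Standard error of a two-arm difference = sqrt(2/10) = 0.447 SD.
2. Shift relative to that: 0.2/0.447 = 0.45; 0.3/0.447 = 0.67.
3. With no true difference, a shift of 0.2 or 0.3 SD raises the false-positive rate of a 5% t test (18 degrees of freedom, noncentral t) to about 7% or 10%.
4. Next-trial size per arm = 2(1.96 + 0.84)²/d², with unrounded normal quantiles giving a numerator of 15.70:
   - d = 0.5: 15.70/0.25 = 62.8, about 63
   - d = 0.5 + 0.2 = 0.7: 15.70/0.49 = 32.0, about 32 (33 if rounded up from 32.04)
   - d = 0.5 + 0.3 = 0.8: 15.70/0.64 = 24.5, about 25
5. Power of those trials at the true 0.5 SD: about 53% with 33 per arm and 42% with 25 per arm, instead of 80%.
6. With a true difference of 0.8 SD, the need is 25 per arm. Planning on 1.0 or 1.1 SD gives 16 or 13 per arm, with power of about 62% or 53%.

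**Can ultrasound reading be masked?** Group A has three scans and Groups B and C have two. For 30 completed subjects that is 10 × 3 + 20 × 2 = 70 scanning sessions. If images are read subject by subject, the third scan identifies Group A, and a reader who has just seen the subject finish may recall the arm. If images carry separate codes and are read in random order after the last subject completes, neither cue remains.

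**The case against.** The case against is substantial, and several parts of it stand.

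- A reader might infer that the person who treats also measures. The documents do not say so: 7.1 names a trained clinician for the garments, and 7.4.10 names trained study staff for the parameters. The plan permits the overlap; it does not state it.
- A reader might infer that expectation favours the heavier regimen. Neither direction nor size is documented. Only Group C is clearly the heaviest, at 20 hours; Group A has 12 hours against Group B's 10, yet B has more sessions per day.
- A reader might extend the concern to the leading outcome. Bioimpedance and perometry are instrument readouts, so the argument is much weaker there.
- The device appendices were not in the supplied text. A masking step could be described in them, so its absence can be asserted only for the text seen.
- Subjects and treating staff cannot practicably be masked, because session patterns, Group C's additional moisture reading and Group A's Day 12 show the arm. Live readings stay unmasked to arm whatever is added.
- Ultrasound has no model in section 8.2, so masking its reading protects nothing until an analysis is named.

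What does not stand is the conclusion that nothing useful can be done. Batch image reading, hiding earlier values and fixing covariates do not depend on masking the visit. Nor does the small, unpowered sample excuse the gap, because the pilot's estimates are meant to shape the next trial.

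**Conclusion.** The point holds in a limited form. In the supplied text, measuring staff are not separated from treating staff, allocation is known before the Day 1 readings, and no masking is described for tonometry, tissue ultrasound, the moisture meter or covariate selection. This can distort the dose contrasts and the endpoint ranking; it is not shown that it will.

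The size rests wholly on the assumed shift. At 0.2 to 0.3 SD it is smaller than the sampling error at 10 per arm, but it is systematic and would pass into the next trial's planning, at about 32 or 25 per arm where 63 are needed if the true difference is 0.5 SD. The remedy removes only part of this. The point is best treated as a cheap improvement, not a flaw that undermines the trial.

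**What to change.** All three changes use existing staff.

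1. **Section 7.4.6:** store ultrasound images under image-level codes. Have the existing reader measure them in random order, in one batch after the last subject completes, masked to arm, subject and time point. Name the ultrasound analysis in 8.2.2.
2. **Sections 7.4.5 and 7.4.7:** record tonometer and moisture-meter readings on a form that does not show earlier values.
3. **Section 8.2:** replace the testing of candidate covariates with a set fixed before arm labels are released to the analyst. Include the endpoint's baseline value wherever it is not already one of the modelled time points.

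State in the protocol and the report that live readings were unmasked to arm, and whether the same staff treated and measured. If an appendix already covers any of this, a cross-reference is enough.

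The cost is protocol wording, coded image files and a revised form, with no additional assessor, visit or procedure. Ultrasound results come later, and image acquisition and live readings remain unmasked to arm.
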